**Table 8. Laboratory Analyte Listing**

Local Lab Chemistry	Local Lab Coagulation	Local Lab Urinalysis	Local Lab Hematology	Local Lab Other Labs	Central Lab Other Labs
Sodium	PTT	Blood	Hemoglobin	IgG	Anti-blinatumomab antibodies
Potassium	INR	Protein	Hematocrit	HIV	Lymphocyte subsets
Chloride	Fibrinogen	Glucose	Reticulocytes	Hepatitis B surface antigen	Cytokines
Total protein			Platelets	Hepatitis B core antibody	PK
Albumin			WBC	Hepatitis C virus antibody	
Calcium			RBC	Urine or serum pregnancy test	
Magnesium			Differential	Bone marrow biopsy a	
Phosphorus			• Neutrophils	Lumbar puncture a	
Glucose			• Bands/stabs		
BUN or Urea			• Eosinophils		
Creatinine			• Basophils		
Uric acid			• Lymphocytes		
Alk phos			• Monocytes		
LDH					
AST (SGOT)					
ALT (SGPT)					
C-reactive protein					
Lipase					
Amylase					
Bilirubin (total)					
GGT					

Abbreviations: ALK phos = alkaline phosphatase; ALT = alanine transaminase; AST = aspartate transaminase; BUN = blood urease nitrogen; GGT = gamma-glutamyl transferase; HIV = human immunodeficiency virus; IgG = Immunoglobulin G; INR = international normalized ratio; LDH = lactic dehydrogenase; PK = pharmacokinetic; RBC = red blood count; SGOT = Serum glutamic oxaloacetic transaminase; SGPT = Serum glutamic pyruvic transaminase; WBC = white blood count.

a Bone marrow and lumbar puncture only required if concerns of disease presence per investigator judgement. A sample of CSF if obtained for grade 3 or higher neurologic event will be obtained for blinatumomab PK (central lab) and other local labs (refer to [Section 7.3.13](#)).

### 7.3.15 Pharmacokinetic Samples

Serum samples will be collected during the blinatumomab treatment in all subjects to measure blinatumomab serum concentration by a validated bioassay. Blood samples

Approved

for PK are outlined in the Schedule of Assessments ([Table 3](#) and [Table 5](#)). Details are provided below:

#### 7.3.15.1 Cycle 1/Period 1

During cIV run-in, PK samples are collected at any time during the day on the second day after the start of the 9 µg/day, 28 µg/day, and 112 µg/day doses, (ie, PK samples are obtained on day 2, day 9, and day 16, respectively).

During SC dosing, PK samples are collected for:

**For SC dosing at q12h, q24h q48h and q96h:**

- **PK samples are collected for the first dose on day 22 (pre-dose, as well as 1 hour ± 15 minutes, 2 hours ± 15 minutes, 4 hours ± 30 minutes, 6 hours ± 30 minutes, 8 ± 1 hours, and 12 ± 1 hours (before the next q12h dose if applicable) and for the last dose on day 26 (pre-dose, as well as post-dose at 1 hour ± 15 minutes, 2 hours ± 15 minutes, 4 hours ± 30 minutes, 6 hours ± 30 minutes, 8 ± 1 hours, 12 ± 1 hours, as well as 24 ± 2 hours (day 27), and 48 ± 2 hours (day 28). (Refer to [Table 3](#) and [Table 4](#)).**

**For SC dosing at q72 hours:**

- **PK samples are collected for the first dose on day 22 (pre-dose, as well as 1 hour ± 15 minutes, 2 hours ± 15 minutes, 4 hours ± 30 minutes, 6 hours ± 30 minutes, 8 ± 1 hours, and 12 ± 1 hour and for the last dose on day 25 (pre-dose, as well as post-dose at 1 hour ± 15 minutes, 2 hours ± 15 minutes, 4 hours ± 30 minutes, 6 hours ± 30 minutes, 8 ± 1 hours, 12 ± 1 hours, as well as 24 ± 2 hours (day 26), 48 ± 2 hours (day 27), and 72 ± 2 hours (day 28) (Refer to [Table 3](#) and [Table 4](#))**

**For the SC dosing at q7days:**

- **PK samples are collected for the dose on day 22 (pre-dose, as well as 1 hour ± 15 minutes, 2 hours ± 15 minutes, 4 hours ± 30 minutes, 6 hours ± 30 minutes, 8 ± 1 hours, 12 ± 1 hour as well as 24 ± 2 hours (day 23), 48 ± 2 hours (day 24), 72 ± 2 hours (day 25) and 96 ± 2 hours (day 26). (Refer to [Table 3](#) and [Table 4](#))**

In the return to cIV dosing following the 5 treatment days of SC administration, PK samples are collected any time during the day on the second day (day 30) after resuming 112 µg/day dose on day 29. See [Table 3 and Table 4](#) for further details. **In addition to the above listed PK samples, PK data will also be collected for adverse events of CTCAE ≥ grade 3 of CRS or neurotoxicity. Obtain the samples as close as possible to the start of the event, at approximately 24 hours after the event and at the end of the event when all symptoms are resolved.**

**PK samples should be drawn peripherally during cIV dosing period.**

### 7.3.15.2 Cycle 1/Period 2

- PK samples are collected for 9 µg/day SC equivalent dose 1 (Monday-Day 1): pre-dose, 1 hour ± 15 minutes, 2 hours ± 15 minutes, 4 hours ± 30 minutes, 6 hours ± 30 minutes, 8 ± 1 hours, and 12 ± 1 hours, 24 ± 1 hours
- PK samples are collected for 9 µg/day SC equivalent dose 2 (Wednesday-Day 3): pre-dose, 1 hour ± 15 minutes, 2 hours ± 15 minutes, 4 hours ± 30 minutes, 6 hours ± 30 minutes, 8 ± 1 hours, and 12 ± 1 hours, 24 ± 1 hours
- PK samples are collected for 28 µg/day SC equivalent dose 1 (Friday-Day 5): pre-dose, 1 hour ± 15 minutes, 2 hours ± 15 minutes, 4 hours ± 30 minutes, 6 hours ± 30 minutes, 8 ± 1 hours, and 12 ± 1 hours, 24 ± 1 hours, 48 ± 1 hours
- PK samples are collected for 28 µg/day SC equivalent dose 3 (Wednesday-Day 10): pre-dose, 1 hour ± 15 minutes, 2 hours ± 15 minutes, 4 hours ± 30 minutes, 6 hours ± 30 minutes, 8 ± 1 hours, and 12 ± 1 hours, 24 ± 1 hours
- PK samples are collected for MTD dose #1 (Friday-day 12): pre-dose, 1 hour ± 15 minutes, 2 hours ± 15 minutes, 4 hours ± 30 minutes, 6 hours ± 30 minutes, 8 ± 1 hours, and 12 ± 1 hours
- PK samples are collected for MTD dose # 2 (as denoted in the schedules for the different options): pre-dose, 1 hour ± 15 minutes, 2 hours ± 15 minutes, 4 hours ± 30 minutes, 6 hours ± 30 minutes, 8 ± 1 hours and 12 ± 1 hours
- PK samples are collected for MTD dose # 3 (as denoted in the schedules for the different options): pre-dose, 1 hour ± 15 minutes, 2 hours ± 15 minutes, 4 hours ± 30 minutes, 6 hours ± 30 minutes, 8 ± 1 hours, 12 ± 1 hours, 24 hr ± 1 hours, and 48 hr ± 1 hours (this is to be obtained pre-dose for q48h option)

See [Table 6](#) for further details.

If doses were interrupted in any days associated with PK sampling, the PK sample collection day will be delayed accordingly until the resumed dose is given.

In addition, PK data will also be collected in the events of CTCAE ≥ grade 3 adverse events of CRS or neurotoxicity that occurs **during SC administration**. **Obtain the samples as close as possible to the start of the event, at approximately 24 hours after the event, and at the end of the event when all symptoms are resolved.**

### 7.3.15.3 Optional Cycle 2/Period 2

Pharmacokinetic, cytokine and lymphocyte subset samples will only be obtained in Optional Cycle 2 for CTCAE ≥ grade 3 adverse events of CRS or neurotoxicity. PK will be collected as close as possible to the start of the event, at approximately 24 hours after the event, and at the end of the event when all symptoms are resolved. Lymphocyte subsets and cytokines will be collected as close as possible to the start of the event and at resolution of the event.

### 7.3.16 Pharmacodynamic Samples

#### 7.3.16.1 Lymphocyte Subsets

Lymphocyte subsets will be measured by flow cytometry for quantification of different markers (eg, T cells: CD3, CD4, CD8; B cells: CD19). The sampling time points are outlined in the Schedule of Assessments ([Table 3](#), [Table 5](#), [Table 6](#), and [Table 7](#)). **In addition, lymphocyte subsets will also be collected for adverse events of CTCAE  $\geq$  grade 3 of CRS or neurotoxicity that occurs during SC administration. Obtain the samples as close as possible to the start of the event and at resolution of the event.**

#### 7.3.16.2 Cytokines

Cytokine samples (IL-6, IL-10, IL 12, interferon gamma [IFN- $\gamma$ ], and tumor necrosis factor alpha) will be measured by the commercially available FACS based BD™ Cytometric Bead Array system. Blood samples will be collected at the time points outlined in the Schedule of Assessments ([Table 3](#), [Table 5](#), [Table 6](#), and [Table 7](#)). **In addition, cytokine data will also be collected for adverse events of CTCAE  $\geq$  grade 3 of CRS or neurotoxicity that occurs during SC administration. Obtain the samples as close as possible to the start of the event and at resolution of the event.**

### 7.4 Antibody Testing Procedures

Blood sample(s) will be collected at time points as outlined in the [Table 3](#), [Table 5](#), and [Table 7](#) for the measurement of anti-blinatumomab binding antibodies. Samples testing positive for binding antibodies will also be tested for neutralizing antibodies and may be further characterized for quantity/titer, isotype, affinity and presence of immune complexes. Additional blood samples may be obtained to rule out anti-blinatumomab antibodies during the study. Subjects who test positive for anti-blinatumomab antibodies and have clinical sequelae that are considered potentially related to an anti-blinatumomab antibody response may also be asked to return for additional follow-up testing.

### 7.5 Biomarker Development

Blood samples will be collected to monitor changes in lymphocytes (B-cell and T-cell populations) and cytokines in peripheral blood.

In addition, biomarker data as described above will also be collected for CTCAE  $\geq$  grade 3 adverse events of CRS or neurotoxicity that occurs throughout the study both at the start and resolution of the event.

## 7.6 Sample Storage and Destruction

Any blood biomarker, PK sample collected according to the Schedule of Assessments (Table 3, Table 4, Table 5, Table 6, and Table 7) can be analyzed for any of the tests outlined in the protocol and for any tests necessary to minimize risks to study subjects. This includes testing to ensure analytical methods produce reliable and valid data throughout the course of the study. This can also include, but is not limited to, investigation of unexpected results, incurred sample reanalysis, and analyses for method transfer and comparability.

All samples and associated results will be coded before the being shipped from the site for analysis or storage. Samples will be tracked using a unique identifier that is assigned to the samples for the study. Results are stored in a secure database to ensure confidentiality.

If informed consent is provided by the subject, Amgen may do additional testing on remaining samples (ie, residual and back-up) to investigate and better understand the relapsed/refractory indolent NHL, the dose response and/or prediction of response to blinatumomab, as required, characterize antibody response, and characterize aspects of the molecule (eg, mechanism of action/target, metabolites). Results from this analysis are to be documented and maintained, but are not necessarily reported as part of this study. Samples can be retained for up to 20 years.

Since the evaluations are not expected to benefit the subject directly or to alter the treatment course, the results of pharmacogenetic, biomarker development, or other exploratory studies are not placed in the subject's medical record and are not to be made available to the subject, members of the family, the personal physician, or other third parties, except as specified in the informed consent.

The subject retains the right to request that the sample material be destroyed by contacting the investigator. Following the request from the subject, the investigator is to provide the sponsor with the required study and subject identification number so that any remaining sample types (eg, blood, tumor) samples and any other components from the cells can be located and destroyed. Samples will be destroyed once all protocol-defined procedures are completed. However, information collected from samples before the request for destruction, will be retained by Amgen.

The sponsor is the exclusive owner of any data, discoveries, or derivative materials from the sample materials and is responsible for the destruction of the sample(s) at the

request of the subject through the investigator, at the end of the storage period, or as appropriate (eg, the scientific rationale for experimentation with a certain sample type no longer justifies keeping the sample). If a commercial product is developed from this research project, the sponsor owns the commercial product. The subject has no commercial rights to such product and has no commercial rights to the data, information, discoveries, or derivative materials gained or produced from the sample. See [Section 11.3](#) for subject confidentiality.

## **8. WITHDRAWAL FROM TREATMENT, PROCEDURES, AND STUDY**

### **8.1 Subjects' Decision to Withdraw**

Subjects have the right to withdraw from the study at any time and for any reason without prejudice to their future medical care by the physician or at the institution.

Subjects (or a legally acceptable representative) can decline to continue receiving investigational product and/or other protocol-required therapies or procedures at any time during the study but continue participation in the study. A legally acceptable representative is an individual or other body authorized under applicable law to consent, on behalf of a prospective subject, to the subject's participation in the clinical study. If this occurs, the investigator is to discuss with the subject the appropriate processes for discontinuation from investigational product, device or other protocol-required therapies and must discuss with the subject the options for continuation of the Schedule of Assessments ([Table 3](#), [Table 4](#), [Table 5](#), [Table 6](#), and [Table 7](#)) and collection of data, including endpoints, adverse events, disease related events, and device related events, as applicable. The investigator must document the change to the Schedule of Assessments ([Table 3](#), [Table 4](#), [Table 5](#), [Table 6](#), and [Table 7](#)) and the level of follow-up that is agreed to by the subject (eg, in person, by telephone/mail, through family/friends, in correspondence/communication with other physicians, from review of the medical records).

Withdrawal of consent for a study means that the subject does not wish to receive further protocol-required therapies or procedures, and the subject does not wish to or is unable to continue further study participation. Subject data up to withdrawal of consent will be included in the analysis of the study, and where permitted, publicly available data can be included after withdrawal of consent. The investigator is to discuss with the subject appropriate procedures for withdrawal from the study.

Approved

## 8.2 Investigator or Sponsor Decision to Withdraw or Terminate Subjects' Participation Prior to Study Completion

The investigator and/or sponsor can decide to withdraw a subject(s) from investigational product, device, and/or other protocol-required therapies, protocol procedures, or the study as a whole at any time before the study completion.

Subjects may be eligible for continued treatment with Amgen investigational product(s) and/or other protocol-required therapies by a separate protocol or as provided for by the local country's regulatory mechanism, based on parameters consistent with [Section 12.1](#).

## 8.3 Reasons for Removal From Treatment or Study

### 8.3.1 Reasons for Removal From Treatment

Reasons for removal from protocol-required IP(s) or procedural assessments include any of the following:

- Protocol-specified criteria: a DLT during the DLT evaluation period (see [Section 6.2.1.2.3](#)), neurological event as described in [Section 6.2.1.4.3](#) and [Appendix E](#)
- Subject request
- Safety concern:
  - due to an adverse event
  - pregnancy
  - ineligibility determined
  - protocol deviation
  - non-compliance
  - requirement for alternative therapy (including transplant),
- Death
- Lost to follow-up
- Decision by sponsor (other than subject request or safety concern, lost to follow)
- Disease progression (eg, clinically relevant disease progression, relapse or non-response) **for subjects in Period 1**

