### 6.2.1.2.3 Dose Limiting Toxicities

All toxicities will be graded using the Common Terminology Criteria for Adverse Events (CTCAE) version 4.0 (see [Appendix D](#)). The occurrence of any of the following toxicities during the DLT evaluation period will be considered a DLT, if judged by the investigator to be related to the administration of blinatumomab:

- Any treatment-related death
- Any treatment-related toxicity, regardless of grade, that leads to a subject's removal from the study by the investigator and/or sponsor
- Persistent CTCAE grade  $\geq 2$  non-hematologic adverse events related to blinatumomab that are deemed intolerable by the subject or the treating physician and that do not respond to appropriate medical management within 5 days and lead to treatment discontinuation will be considered DLTs
- Recurrent grade 2 seizures ie, brief generalized seizures
- All grade 3 and 4 adverse events and laboratory abnormalities, which occur during the SC administration portion of the treatment period and which, in the opinion of the investigator, are at least possibly related to the investigational drug, are considered as DLT with exceptions noted below:
  - Laboratory parameters of grade  $\geq 3$  that responds to intervention/treatment interruption and resolves to grade  $\leq 1$  within 7 days
  - **Grade 3 and 4 lymphopenia**
  - Grade 3 fever or infection
  - Grade  $\leq 3$  events of CRS or tumor lysis syndrome that responds to intervention/treatment interruption and resolves to grade  $\leq 1$  within 7 days
  - **Grade 3 neurologic events that respond to intervention/treatment interruption and resolves to grade  $\leq 1$  within 7 days**

Approved

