Restart cIV infusion should be performed with a 9/28/112 µg/day weekly dose escalation if last dose given was 9 or 28 µg/day. If last dose given was 112 µg/day restart should be performed with a 28/112 µg/day dose escalation (dose escalation 1 week after restart).

For SC dosing, the doses that have equivalent exposures to the cIV doses mentioned above should be used.

Restart and dose escalation for cIV infusion and SC should be performed in the hospital, under supervision of the investigator and the subject should be hospitalized for 48 hours.

In addition, to the events described above, the dose may be temporarily or permanently reduced to 9 µg/day cIV infusion (or the equivalent SC dose) if, by the investigator's judgment, it is necessary for safety reasons. After at least 7 days of dosing at 9 µg/day cIV infusion (or the equivalent SC dose), the dose may be increased to 28 µg/day cIV infusion (or the equivalent SC dose) or treatment may be continued at the dose of 9 µg/day cIV infusion (or the equivalent SC dose) after consultation with an Amgen medical monitor. Likewise, if an event occurred at a dose of 112 µg/day cIV infusion or the SC MTD, the dose may be temporarily or permanently reduced to 28 µg/day cIV infusion (or the equivalent SC dose) and may be increased to 112 µg/day cIV infusion (or SC MTD) following the same guidance as described above. This does not apply for neurologic events (refer to [Table 2](#)).

Detailed instructions for blinatumomab interruption and re-start instructions for CRS, neurotoxicity, hepatotoxicity, and other clinically relevant adverse events are detailed in [Table 2](#).

Approved

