Other clinically relevant adverse events	Grade 3	
 
○ Interrupt blinatumomab until <math>\leq</math> grade 1
 
○ Restart no less than 72 hours after the initial observation of the grade 3 event at the following dose levels:
 
 
For cIV infusion
 
 
○ If event occurred at 112 <math>\mu</math>g/day, resume cIV infusion at 28 <math>\mu</math>g/day
 
○ If event occurred at dose of 9 <math>\mu</math>g/day or 28 <math>\mu</math>g/day, resume cIV infusion at 9 <math>\mu</math>g/day
 
○ Escalate up 1 dose level after 7 days if toxicity does not reoccur. Increase dose stepwise at 7-day intervals to target dose of 112 <math>\mu</math>g/day if toxicity does not re-occur
 

Approved

Abbreviations defined on last page of the table.

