**Table 2. Treatment Interruptions and Restart**

Toxicity	Grade	Instructions for Treatment Interruptions and Restart
Other clinically relevant adverse events (continued)	Grade 3	
For SC week 4 Period 1/Cycle 1
 
 
○ Resume at 28 µg/day cIV infusion.
 
○ Escalate up after 7 days if toxicity does not reoccur to 112 µg/day cIV infusion for 7 days.
 
○ Hold cIV infusion for 12 hours if toxicity did not reoccur
 
○ Resume with the day SC that toxicity occurred at the dose of that cohort (i.e if toxicity occurred on day 23 then resume SC on day 23 of cycle and repeat all labs that are written for this day on Schedule of Assessments).
 
 
For SC Period 2:
 
 
○ If event occurred at MTD SC, resume SC at 28 µg/day equivalent SC
 
○ If event occurred at 28 µg/day SC equivalent, resume SC at 9 µg/day SC equivalent
 
○ Escalate up 1 dose level after 7 days if toxicity does not reoccur. Increase dose stepwise at 7-day intervals to MTD SC
 
 
 
● Permanently discontinue blinatumomab if:               
 
○ Initial grade 3 event does not improve to grade ≤ 1 within 14 days, OR
 
○ Grade 3 event reoccurs at the lower dose level within 7 days of re-initiation, OR
 
○ Grade 3 event reoccurs at a dose of 9 µg/day cIV (or the equivalent SC dose) without prior step-dose escalation
 
 
 

	Grade 4	Permanently discontinue for non-laboratory adverse events at least possibly related to blinatumomab

Page 4 of 4

Abbreviations: ALP = alkaline phosphatase; ALT = alanine aminotransferase; AST = aspartate aminotransferase; cIV = continuous intravenous; CRS = cytokine release syndrome; INR = international normalized ratio; MRI = magnetic resonance imaging; **MTD = maximum tolerated dose**; RUQ = right upper quadrant; SC = subcutaneous; TBL = total bilirubin level; ULN = upper limit of normal.

Biomarker samples, as described in [Section 7.5](#), will also be collected for grade ≥ 3 neurologic adverse events or grade ≥ 3 CRS that occur in all periods of the study at the start of the adverse event and at the time of resolution of the adverse event.

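### Section 8.3.1 removes a subject who has a DLT, but the Table 2 row for other grade 3 events has no DLT carve-out and would return the same subject to SC dosing

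*Protocol*

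**What the plan says.** **DLT definition (Protocol 6.2.1.2.3).** Grade 3 and 4 events during SC administration that, in the investigator's opinion, "are at least possibly related to the investigational drug, are considered as DLT with exceptions noted below". The exceptions are:
- laboratory abnormalities that settle to grade 1 or less within 7 days
- lymphopenia
- grade 3 fever or infection
- CRS, tumor lysis syndrome and grade 3 neurologic events that settle within 7 days

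**Removal (Protocol 8.3.1).** The first listed reason for removal from treatment is "Protocol-specified criteria: a DLT during the DLT evaluation period", with no minimum number of DLTs in the cohort. Section 6.2.1.4.3, whose lead-in refers to 8.3.1, requires permanent discontinuation for an adverse event that meets the protocol's own safety criteria. Section 3.4.2 speaks of Period 2 subjects taken off for a DLT as a group that is never replaced.

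**Restart (Protocol 6.2.1.4.2 and Table 2).** Section 6.2.1.4.2 states: "Detailed instructions for blinatumomab interruption and re-start instructions for CRS, neurotoxicity, hepatotoxicity, and other clinically relevant adverse events are detailed in" Table 2. The grade 3 row for other clinically relevant adverse events (the Other row below) interrupts treatment until grade 1 or less, then says "Restart no less than 72 hours after the initial observation of the grade 3 event at the following dose levels".
- In week 4 of Period 1 the subject receives cIV at 28 and then 112 µg/day. The row continues "Hold cIV infusion for 12 hours if toxicity did not reoccur" and then "Resume with the day SC that toxicity occurred at the dose of that cohort".
- In Period 2 the subject resumes at a lower SC equivalent dose, with the instruction "Increase dose stepwise at 7-day intervals to MTD SC".
- Treatment ends permanently if "Initial grade 3 event does not improve to grade ≤ 1 within 14 days", or on specified recurrences. Being a DLT is not a trigger.

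**Cohort rule (Protocol 3.1.1 and 6.2.1.2.2; SAP 8.1.1.2).** Dosing stops for the individuals with a DLT where 2 or more of 6 evaluable subjects have one. The branch for 1 or fewer says nothing about the affected subject. The Period 2 part of 6.2.1.2.2 has no individual stop.

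**The concern.** A related grade 3 event outside the exceptions, occurring in the SC week, meets the DLT definition and the removal criterion, and also falls under a Table 2 row that tells the site how to resume SC. No sentence ranks one over the other or limits the row to events that are not DLTs. Two sites facing the same single DLT could act in opposite ways, and a subject's further SC dosing could turn on whether someone else in the cohort has a second DLT.

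Section 3.1 describes this as the first human use of the SC route, so what is at stake is patient safety and uniform conduct. Whether cIV may continue is open too: 8.3.1 concerns removal from investigational product, while the Period 1 SC block of Table 2 resumes cIV first.

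**Working it through.** **1. Which events fall under both rules.** Taking the DLT exceptions against the rows of Table 2:
- *In the overlap:* related grade 3 non-laboratory events outside the exceptions, however quickly they settle; and tumor lysis syndrome or non-hepatic laboratory events (other than lymphopenia) that take more than 7 but no more than 14 days to settle.
- *Outside it:* events covered by a DLT exception; hepatic laboratory events (own row and Section 6.3); grade 4 non-laboratory events (permanent stop); CRS and neurologic events (own rows).

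For grade 3 CRS and neurologic events, Table 2 stops treatment permanently if there is no recovery within 7 days, the same 7 days as in the DLT exception. Rechallenge there goes with not being a DLT. The Other row allows 14 days and has no matching exception, so the mismatch is largely confined to it.

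**2. Earliest return to SC in Period 1.** 72 hours + 7 days at 28 µg/day + 7 days at 112 µg/day + 12-hour hold = 3 + 7 + 7 + 0.5 = 17.5 days after the event.

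**3. Earliest return to the MTD in Period 2.** For an event at the MTD: 72 hours + 7 days at the 28 µg/day equivalent = 3 + 7 = 10 days. For an event at the 28 µg/day equivalent: 3 + 7 + 7 = 17 days.

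**4. Size of re-exposure in Period 1.** Table 2's own example is an event on day 23. I take the 9 q12h doses as two on each of days 22 to 25 and one on day 26, and the q24h doses as one a day.
- Cohort 1: 7 of 9 doses, 7 × 112 = 784 µg
- Cohort 2: 7 of 9 doses, 7 × 225 = 1,575 µg
- Cohort 3: 4 of 5 doses, 4 × 450 = 1,800 µg

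Under removal the figure is none. The longer-interval regimens have fewer week 4 doses to repeat: Table 4 shows 3 (q48h), 2 (q72h), 2 (q96h) and 1 (q7d).

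**5. How often a cohort could meet the question.** Protocol 10.2 gives 89% and 42% for 1 or fewer DLTs in 6 at true rates of 10% and 30%. These reproduce:
- 0.9^6 + 6 × 0.1 × 0.9^5 = 0.531 + 0.354 = 0.886
- 0.7^6 + 6 × 0.3 × 0.7^5 = 0.118 + 0.303 = 0.420

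The question arises at any overlapping DLT, including the first in a cohort that later has two. The ceiling is therefore the probability of at least one DLT:
- 10%: 1 − 0.9^6 = 1 − 0.531 = 0.469, or 47%
- 30%: 1 − 0.7^6 = 1 − 0.118 = 0.882, or 88%

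The cohorts that end with exactly one DLT, where no express individual stop ever applies, are the second terms above: 35% and 30%.

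**The case against.** The best defence is a harmonised reading. Section 6.2.1.4.3 makes protocol safety criteria a ground for permanent discontinuation and refers to 8.3.1, where a DLT comes first. Section 3.4.2 assumes removal. The Other row is generic: it covers both routes and related and unrelated events alike, and nobody would take its silence on, say, prohibited medication as overriding that stop. It still has work to do if confined to events that are not DLTs. The Amendment 6 rationale took quickly resolving grade 3 neurologic events out of the DLT definition and in the same amendment added SC rechallenge for them, which suggests rechallenge was meant for non-DLT events.

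Much of this stands. A reader might infer that nothing in the protocol indicates which rule should prevail. That goes too far, since the surrounding text favours removal. But it does so by inference only; 8.3.1 is framed as a list of reasons rather than an instruction, and the table sites are sent to for restart does not exclude DLTs.

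A reader might also picture the causative dose being given straight back. The documents do not support that. Restart needs recovery to grade 1 or less and at least 72 hours. Section 6.2.1.4.2 requires supervised restart with 48 hours in hospital. Period 1 adds two weeks of cIV, and Section 6.2.1.1.4 keeps Period 1 subjects in hospital throughout SC dosing. Recurrence at the lower dose level within 7 days of re-initiation ends treatment. These steps reduce the risk without saying which rule applies.

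Finally, 35% and 30% might be taken as the upper limit on affected cohorts. They are not, because a site must act on the first DLT before anyone knows whether a second will follow.

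**Conclusion.** The inconsistency is real but narrow, and it should be corrected. For a related, non-exempt grade 3 event that settles to grade 1 or less within 14 days, a site following Table 2 as written would re-expose to SC a subject whom 8.3.1 removes. Only where 2 or more of 6 have a DLT does an express sentence stop that subject's dosing.

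The per-cohort ceiling is 47% at a true DLT rate of 10% and 88% at 30%, assuming six independent evaluable subjects with a common rate. The documents do not give the share of DLTs in the overlap, so the actual frequency is lower by an unknown amount. The dose totals illustrate one event day in the three named cohorts; later cohorts on longer intervals would see fewer repeat doses.

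A reader might infer that the DLT count or the MTD is biased. It is not. The subject counts as having a DLT from the event itself, whatever happens afterwards, so the 2-of-6 rule, the MTD definition and the Period 2 boundaries in Table 10 work identically under either reading. The consequence is for patient safety and consistent handling across sites.

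**What to change.** 1. **Table 2, Other row, grade 3, both SC blocks (Period 1 and Period 2):** add *SC is not restarted if the event meets the DLT definition in Section 6.2.1.2.3; see Section 8.3.1.*
2. **Protocol 6.2.1.2.2:** state that a DLT ends SC dosing for that subject, whatever the number of DLTs in the cohort. Mirror the sentence in SAP 8.1.1.2, for consistency only.
3. **Protocol 8.3.1:** the sponsor should decide and state whether cIV may continue after a DLT. This is a clinical choice that the documents do not settle. The text after Table 2 that allows cIV completion concerns cohort members who have not yet reached SC, so it does not answer the question for a subject with a DLT.

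The cost is a few sentences, with no extra subjects or procedures. The downside is that a few subjects lose SC rechallenge after a resolved grade 3 event, and some SC PK data are lost.
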